University of South Florida

Protocol for Clinical Investigation

I. Summary

1. Title: Evaluation of a novel solution, IRRISEPT™, a new delivery system, containing a long-acting antimicrobial agent for irrigation of skin and soft tissue infections, in the form of an abscess, in the emergency department: a pilot study

2. Sponsor:

IRRIMAX Corporation

3. Clinical phase:

Phase III Pilot Study

4. Duration of the study: January 2010 - December 2011

5. Methodology:

This is a prospective randomized controlled clinical trial.

6. Study site:

Emergency Department, Tampa General Hospital

7. Number of subjects: 200 patients

8. Principal investigator: [name].

Director, Emergency Medicine Research Department Tampa General Hospital – University of South Florida

[name]

[name] (O) [contact]

9. Co-investigators:

[name], PhD

[name], MS

10. Study coordinator:

[name], BPharm

1 of 9 Updated: 30AUG2010

II. List of abbreviations

ACEP American College of Emergency Physicians

CHG chlorhexidine gluconate

ED Emergency Department

IRRISEPT™ Wound Debridement and Cleansing System

MRSA Methicillin-Resistant Staphylococcus Aureus

SSTI Skin and soft tissue infection

TGH Tampa General Hospital

USP United States Patent

Updated: 30AUG2010 2 of 9

III. Background

1. Significance of study

Skin and soft-tissue infections (SSTIs), including cutaneous abscesses, surgical site infections, and infected traumatic lesions, are commonly encountered among patients presenting for treatment in emergency departments (ED). While the available literature does not support the use of systemic antibiotic prophylaxis in emergency medicine practice [1-3], most experts recommend irrigation to decrease the rate and prevent the spread of infection, although the clinical significance of irrigation is not known [3,4].

The purpose of irrigation and cleansing is to remove debris, bacteria, and loose tissue. To be effective, the mechanical force used must exceed that of the adhesive forces of the contaminant. Low-pressure irrigation removes negligible small particles but cannot remove large particulate matter, such as devitalized tissue. However, when irrigating solutions are applied at high pressure, destruction of vital tissue may occur. The use of a self-contained irrigation device that can produce sufficient pressure may help standardize care and reduce the progression of infections.

Methicillin-resistant Staphylococcus aureus (MRSA) emerged in the 1960s as a cause of infection among patients exposed to the bacteria in health care settings. During the past decade, MRSA infections have been reported among persons without such exposure (community-associated MRSA) [5-7]. Community-associated outbreaks of MRSA infection have occurred among prisoners, intravenous-drug users, athletes, military trainees, low socioeconomic groups, children, and homosexual men [8-10]. MRSA has primarily been described as a cause of SSTI [10,11]. The number of ED visits for SSTIs has significantly increased in the past decade primarily due to a dramatic increase in the number of infections caused by community-associated MRSA [12]. Therefore, it is crucial to determine MRSA colonization in a population studied for SSTI rates.

Community-associated MRSA has changed the way physicians treat SSTIs. Based on clinical suspicion and on the prevalence of MRSA in certain populations, physicians now are treating these infections (e.g. cutaneous abscesses) with MRSA sensitive antibiotics. This has not been the standard of care and the use of oral antibiotics in treating MRSA associated abscesses has not been confirmed. Irrigation during abscess treatment has been used as an alternative and the self-contained irrigation device may obviate the need for systemic antibiotic coverage.

Updated: 30AUG2010 3 of 9

2. Device description

IRRISEPT™ Wound Debridement and Cleansing System (IRRISEPT) is a manual, self-contained irrigation device that is capable of producing 7-8 psi of pressure as recommended by American College of Emergency Physicians (ACEP) for effective wound cleansing/irrigation. This pressure is sufficient to agitate, loosen and remove debris from wounds. The device has an option for use with a standard irrigation tip or an abscess irrigation tip. The ingredients of the solution are 0.05% Chlorhexidine Gluconate (CHG) in Sterile Water for Irrigation, USP (99.95%). The mechanical action effectively loosens and removes debris. The CHG acts as a preservative to help inhibit microbial growth in the solution.

IV. Objectives

1. Primary objective

The purpose of this pilot study is to provide estimates for sample size calculations for future determination whether IRRISEPT™ with the abscess irrigation tip, can effectively prevents the progression of SSTIs, in the form of an abscess, as compared to treatment by current standard of care utilized in the TGH ED.

2. Secondary objective

The study also aims at determining overall prevalence of MRSA colonization in the studied population.

V. Design

Potential subjects will be recruited through the TGH Emergency Department. Patients presenting with SSTIs will be approached for screening purposes. Once deemed eligible, informed consent will be obtained and the patient will sign the appropriate paperwork for photography and participation in the study.

Randomization methodology will be controlled by a USF biostatistician, following which pertinent history data will be recorded on the study data collection instrument.. In addition to any samples taken by the treating ER physician, a nasal swab for determination of MRSA-colonization status, and a wound culture will be taken and sent to a central lab. A digital photo of the infected site will be obtained at the initial treatment and 48 hour follow-up.

Updated: 30AUG2010 4 of 9

Subjects will have their abscess treated either by **Usual Care** (according to treating physician instructions) or utilizing **IRRISEPT™**, abscess irrigation device as per manufacturing instructions (as below):

Step 1: Attach the Long Tip SplatterGuard (LTSG) to the IrriSept bottle. Insert the tip into the abscess through the incision. Squeeze firmly and empty bottle contents, ensuring that the abscess is thoroughly flushed.

Step 2: Wait 1 minute

Step 3: Attach the LTSG to the IrriRinse bottle. Insert the tip into the abscess through the incision. Squeeze firmly and empty bottle contents, ensuring that the abscess is thoroughly flushed.

Other aspects of care including the use of plain packing and oral antibiotics will be at the discretion of the treating physician in both arms.

Contact information will be obtained and subjects will be instructed to return for a wound check at a point approximately 48 hours after ED discharge; they will also be offered the opportunity to return at any time in event of problems or questions.

The primary end-point of the study is progression of signs and symptoms of infection 48 hours post initial treatment. On follow-up, a blinded investigator will examine the wound for clinical signs of infection (erythema, inflammation, itching, fluctuance, drainage, pain, and a second digital photograph of the site will be taken. The natural progression of the wound at hour 48 will be determined during data analysis as:

- 1.) Improved and healing well
- 2.) Required additional follow-up
- 3.) Required additional treatment

If signs of infection are present at the 48 hour follow-up visit, subjects will be referred to treatment from their primary physician or to the TGH ED.

In the event that subjects do not return for arranged follow-up at 48 hours, a telephone reminder will be made, and a telephone survey will be conducted to determine whether the subject might identify signs of infection. If subjects return subsequent to the phone reminder, their clinical condition will be recorded and used on follow-up visit. In the event that they do not return, the telephone survey result will be employed as the follow-up instrument. Subjects lost to all follow-up will be excluded from further analysis.

Secondary end-point of the study is MRSA colonization as determined by collecting nasal swab specimens obtained during initial patient contact (Baseline visit).

Updated: 30AUG2010 5 of 9

1. Source of research material

Research material for this study includes clinical data (medical history and physical examination, results of laboratory and radiographic tests, consultant's clinical records), nasal cultures for MRSA, and possible wound cultures obtained on follow-up if wound infection identified.

2. Instrumentation

Instruments include standard physician interview and examination, laboratory microbiology studies using existing credentialed clinical support facilities.

VI. Patient enrollment

1. Inclusion criteria

- i. Age 18 to 80
- ii. SSTIs, in the form of an abscess, which will require incision and drainage. Patient able to provide an informed consent
- iii. Patient volunteers to participate

2. Exclusion criteria

- i. Wound was caused by human or animal bite
- ii. Wound is a blunt crush injury or has tendon, bone, or joint involvement
- iii. Diabetic foot infection
- iv. Anticipated incision size less than 5mm
- v. Abscess extends to the muscle layer
- vi. Admission to hospital for any reason, including IV antibiotics
- vii. Clinical signs of systemic infection on initial patient encounter
- viii. Prior history of allergy or hypersensitivity to CHG
- ix. Neutropenic (known ANC<500/mm3), HIV (known CD4<50), or other severely immunocompromised state (e.g. receiving chemotherapy)
- x. Pt is diagnosed with systemic lupus erythematosus or other immunological disease
- xi. Currently in police custody
- xii. Patient withdraws from participation
- xiii. Patient unable or unwilling to give informed consent

3. Recruitment

Any patient meeting inclusion criteria as defined above will be eligible for enrollment. Patients will be briefed on study, informed consent will be sought, and if conferred, subjects will be enrolled.

Updated: 30AUG2010 6 of 9

4. Number of subjects to enroll

Due to the descriptive nature of this pilot study, sample size calculations have not been conducted. We plan to enroll 200 patients total (100 in each study arm) in order to determine the overall prevalence of MRSA colonization in this population and to provide estimates for sample size calculations for future evaluation of non-complicated SSTI, in the form of an abscess, irrigation with IRRISEPT versus usual care. We will perform interim analysis when 100 subjects (or 50 subjects per arm) have been enrolled.

VII. Risks

Participants will receive appropriate and standard care for their presenting condition. Standard risks from participation would be the same as those for patients receiving emergency treatment for their presenting diagnosis: bleeding, infection, adverse reaction or side effect from wound irrigation, pain. There may be risk of a topical irrigation or allergic reaction to CHG. Investigators will be at risk for exposure to contaminated body fluids and tissues; this risk will be minimized by thorough observance of standard precautions. We are unaware of any additional risks imposed by participation in this study.

VIII. Data collection

All pertinent data on initial contact and follow-up will be recorded on the IRRISEPT™ ABSCESS STUDY – Data Collection Form. After completion, data sheets will be collected and data will be entered in a Microsoft Excel database for further evaluation. Only the principal investigator, the co-investigators and the study coordinators will have access to the database. No data with subject identifiers will be released.

IX. Statistical analysis

Descriptive statistics will be reported as means and standard deviations for continuous variables and as frequencies and percentages for categorical variables. No formal analytic statistics are planned for this pilot study.

X. Conflict of interest

This study is sponsored by IRRIMAX Corporation. We are unaware of any conflict of interest.

Updated: 30AUG2010 7 of 9

XI. Duration of study

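### As Section V reads, the arm can be known before the incision is made, so the extent of incision and drainage may differ by arm and would go unmeasured

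*Combined protocol and SAP*

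**What the plan says.** Section V (Design) sets out the sequence in prose. Consent comes first: "Once deemed eligible, informed consent will be obtained and the patient will sign the appropriate paperwork for photography and participation in the study". The next paragraph turns to allocation: "Randomization methodology will be controlled by a USF biostatistician, following which pertinent history data will be recorded on the study data collection instrument". The nasal swab, wound culture and photograph follow, and then the two treatments.

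The eligibility criteria look forward to the procedure. Section VI.1, item ii, admits "SSTIs, in the form of an abscess, which will require incision and drainage", and Section VI.2, item iv, excludes "Anticipated incision size less than 5mm".

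The device instructions in Section V start once an incision exists. Steps 1 and 3 each tell the operator: "Insert the tip into the abscess through the incision. Squeeze firmly and empty bottle contents". Step 1 uses the IrriSept bottle and Step 3 the IrriRinse bottle. Usual care follows the treating physician's instructions and has no corresponding step. The plan adds: "Other aspects of care including the use of plain packing and oral antibiotics will be at the discretion of the treating physician in both arms".

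On masking, Section V says: "On follow-up, a blinded investigator will examine the wound for clinical signs of infection". Nobody else is described as blinded. Section VIII (Data collection) says that pertinent data go on a data collection form; the form itself is not among the documents.

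**The concern.** Every subject has an incision and drainage, and it is not the tested treatment. If the person doing it knows the arm, and in one arm must then pass a tip through the cut and flush the cavity, the length of the cut or the thoroughness of drainage may follow the assignment. This is performance bias in a shared procedure. The blinded 48-hour examination does not protect against it, because the wounds would truly differ. A larger sample would not shrink it either.

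What is at stake is the purpose given in Section IV.1: estimates for sizing a later comparison of IRRISEPT with standard care. Any part of the observed difference that came from the drainage would be carried into that calculation as device effect. If the later trial kept the same order, the same contribution would recur. Without recorded incision length, nobody could tell afterwards whether it had happened.

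**Working it through.** **1. What the text establishes**

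| Question | Source | Finding |
|---|---|---|
| Is the cut still ahead at eligibility? | VI.1 item ii; VI.2 item iv | Yes: drainage is future, incision size is anticipated |
| When is the arm assigned? | V | After consent and before history, by order of the text; no sentence fixes the moment relative to the cut |
| Is the operator masked? | V | Not described as masked; a two-bottle device against usual care can hardly be hidden from its user |
| Does one arm depend on the incision in a way the other does not? | V, Steps 1 and 3 | Yes, IRRISEPT only |
| Is incision and drainage standardised? | V | No |
| Is actual incision length recorded? | V, VIII | Not explicitly required |
| Is there a limit on incision size? | VI.2 item iv | A 5 mm floor on the anticipated size, in both arms |

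Nothing in the plan prevents the arm from being known at the cut, and nothing stated would show whether it mattered.

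**2. Scale of a possible contribution**

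Section VI.4 gives 100 per arm (100 + 100 = 200) with no sample size calculation, so there is no planning figure to reproduce. The rates below are assumptions; none is in the documents.

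Suppose a poor 48-hour outcome occurs in 20% with the usual cut and 12% with a longer cut or fuller drainage, and the device steps have no effect. If knowing the arm changes the drainage in a share s of IRRISEPT subjects, the difference is s × (20 − 12) points. The standard error at 100 per arm is √[p₁(1−p₁)/100 + p₂(1−p₂)/100].

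| s | Rates | Difference | Standard error |
|---|---|---|---|
| 0.25 | 20% v 18% | 2 points | √(0.0016 + 0.001476) = 5.5 points |
| 0.50 | 20% v 16% | 4 points | √(0.0016 + 0.001344) = 5.4 points |
| 0.75 | 20% v 14% | 6 points | √(0.0016 + 0.001204) = 5.3 points |

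The first two are below one standard error and the third slightly above. For comparison, the 95% half-width of a difference at 100 per arm, 1.96 × √[2p(1−p)/100], is 11.1 points at p = 20% and 12.7 points at p = 30%.

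**3. Effect on the future trial's size**

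Assume a true benefit of 10 points, and let drainage add 0, 2 or 5 points. With a two-sided 5% level, 80% power and equal arms:

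n per arm = [1.96 √(2p̄(1−p̄)) + 0.8416 √(p₁(1−p₁) + p₂(1−p₂))]² / (p₁ − p₂)², where p̄ is the mean of p₁ and p₂.

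Example, 20% v 10%: [1.96 × 0.505 + 0.8416 × 0.500]² / 0.01 = 199.

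| Usual-care rate | Observed difference | n per arm planned | Power for the true 10 points |
|---|---|---|---|
| 20% | 10 | 199 | 80% |
| 20% | 12 | 131 | 62% |
| 20% | 15 | 76 | 41% |
| 30% | 10 | 294 | 80% |
| 30% | 12 | 198 | 63% |
| 30% | 15 | 121 | 43.5% |

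The sign could be the other way. Pain, erythema and drainage are among the signs examined at 48 hours, so a larger wound might score worse. If 5 points were lost, the observed difference would be 5 points and the same formula plans 906 per arm (20% v 15%) or 1,251 per arm (30% v 25%), instead of 199 or 294.

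**The case against.** The strongest case against has four parts.

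*The timing is inferred.* No sentence says when the assignment is opened relative to the cut. Section V is not a strict timeline: it mentions the 48-hour photograph before describing treatment. This stands. A reader might conclude that the protocol stipulates randomisation before drainage; it does not. It is only the natural reading, and nothing rules it out.

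*The mechanism is not documented.* No tip diameter is given, and nothing says the device needs a larger cut than usual. The 5 mm floor applies to both arms and reduces any need to enlarge the cut. This also stands, so a reader who infers that IRRISEPT subjects must be cut longer goes beyond the text. But the floor concerns an anticipated size. It does not govern what is cut once the arm is known, nor how fully the cavity is drained.

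*The trial never set out to isolate irrigation.* Section IV.1 compares the device with current standard of care. Usual care is undefined and may itself include irrigation, which Section III.1 says most experts recommend. Packing and oral antibiotics are discretionary in both arms. Any access the device needs could be counted as part of the device strategy. This defeats the stronger reading that the order of events is what stops the arm difference from isolating irrigation: it would not be isolated in any case. It does not defeat the narrower point. The device steps begin after the incision, and if the sponsor regards a different incision as part of the strategy, the plan should say so and measure it.

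*The remedy is incomplete.* After a later reveal the physician could still extend the cut or drain further. That is true, and it is why any later extension must also be recorded.

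**Conclusion.** The concern holds in a limited form. On the natural reading of Section V, an unmasked physician can know the arm when performing a shared, non-standardised procedure whose result only one arm's next step depends on. A difference in incision or drainage between arms is possible and, on the documents as they stand, could be neither excluded nor described.

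The documents do not show that such a difference will occur, which way it would act, or how large it would be. The 2 to 6 points, and the fall in future power from 80% to between 41% and 63%, rest on assumed rates and an assumed favourable direction. Section IX plans descriptive statistics only, so no formal conclusion is at risk in the pilot. The risk is to the estimates it hands on. The case for the change is that it closes most of one bias route at very little cost; it does not show that the pilot is uninterpretable.

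**What to change.** Rewrite the sequence in Section V as follows:

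1. Consent.
2. Baseline history, photograph and samples.
3. Incision and drainage completed by the treating physician as judged necessary, with the actual incision length recorded.
4. The concealed assignment opened (by sealed envelope or call), then IRRISEPT or continued usual care.
5. Any extension of the cut after the assignment is opened recorded in both arms.

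Add to Section IX that incision length and any later extension will be reported by arm; this fits the descriptive analysis already planned. If the form already captures incision length, only the later extension needs adding.

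If re-ordering proves impractical, recording actual incision length and extent of drainage in both arms and reporting them by arm would at least make an imbalance visible.

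The cost is a re-ordered paragraph, an entry on the form, a short pause at the bedside, and a device kit at hand for each enrolled subject. The change needs no extra visit or patient and prescribes no incision technique. It leaves discretionary packing, antibiotics and usual-care irrigation as they are.

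### The 48-hour examination is blinded, but the three-level primary outcome is left to data analysis with no stated rule or masking, and no level is identified as progression

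*Combined protocol and SAP*

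**What the plan says.** Section V (Design) defines the end-point: "The primary end-point of the study is progression of signs and symptoms of infection 48 hours post initial treatment". It masks one step, because at follow-up "a blinded investigator will examine the wound for clinical signs of infection", and a second photograph is taken. The next sentence moves classification to a later stage: "The natural progression of the wound at hour 48 will be determined during data analysis as", followed by three levels: (1) improved, (2) further follow-up required, (3) further treatment required.

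Other passages bear on how that category might be reached:

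- Referral, Section V: "If signs of infection are present at the 48 hour follow-up visit, subjects will be referred to treatment". The sentence is not tied to any of the three levels.
- Telephone follow-up, Section V, for subjects who do not come back: "In the event that they do not return, the telephone survey result will be employed as the follow-up instrument". No mapping from the answers to the three levels is given.
- Section VIII (Data collection): "All pertinent data on initial contact and follow-up will be recorded on the" study's Data Collection Form, which is then entered in an Excel database. On access: "Only the principal investigator, the co-investigators and the study coordinators will have access to the database".
- Section VI.4: "We will perform interim analysis when 100 subjects (or 50 subjects per arm) have been enrolled".
- Section IX: categorical variables are reported as frequencies and percentages, with no formal analysis.

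Section IV gives the pilot's purpose as supplying estimates for sizing a later comparison of progression between the device and usual care.

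**The concern.** Masking protects a reported variable only if it covers every step that needs judgement. Here it is stated for the examination and for nothing after it. The listed signs (erythema, inflammation, itching, fluctuance, drainage, pain) do not convert mechanically into the three levels. Levels 2 and 3 describe care that was required, not change in signs, and there is no level for unchanged or worse. Unless a rule exists elsewhere, someone has to decide the borderline cases after the blinded step.

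The progression rate by arm is the pilot's main product. If borderline cases were settled by someone who knew the arm, the difference between arms could move for reasons other than treatment. Such a shift would be systematic, and no confidence interval would show it. The interim analysis adds a second opening, since nothing says that the rule or the categories are fixed before results are first seen.

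A smaller gap goes with it: a reader cannot tell whether progression means level 3 alone or levels 2 and 3 together.

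**Working it through.** **1. What can be reproduced.** The plan gives no rates, alpha, power or effect size, and says that no sample size calculation was made. Only the counts can be checked: 2 × 100 = 200 enrolled, and 2 × 50 = 100 at the interim analysis. Both agree.

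**2. The text, step by step.**

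| Step | Who | Rule stated | Masking stated |
|---|---|---|---|
| 48-hour examination | blinded investigator | list of signs | yes |
| Telephone survey | not stated | none linking answers to levels | no |
| Assignment of level 1, 2 or 3 | not stated | none | no |
| Choice of level(s) counted as progression | not stated | none | not applicable |

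**3. Hypothetical size of an assignment shift.** Every rate here is an assumption. Suppose 10% of an arm is borderline between two levels and 10%, 20% or 30% of those are placed differently in one arm only. The shift is 0.10 × 0.10, 0.20 or 0.30 = 1, 2 or 3 points, that is 1 to 3 subjects per 100.

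The sample size per arm (80% power, two-sided 5%), with p̄ the mean of p1 and p2, is

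n = [1.960·√(2p̄(1−p̄)) + 0.8416·√(p1(1−p1) + p2(1−p2))]² / (p1−p2)²

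For 25% versus 15%: p̄ = 0.20, so n = [1.960·√0.32 + 0.8416·√0.315]² / 0.01 = 1.581² / 0.01, which gives 250.

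The power column is for the true 25% versus 15% at each n: Φ[(0.10·√n − 1.960·√0.32) / √0.315].

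| Observed | n per arm | Power for true 25% vs 15% |
|---|---|---|
| 25% vs 15% | 250 | 80% |
| 25% vs 14% | 203 | 71% |
| 25% vs 13% | 167 | 63% |
| 25% vs 12% | 139 | 55% |

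A shift the other way, to 16%, 17% or 18%, gives n = 315, 406 or 540.

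**4. Sensitivity to how the future trial is sized.** The figures in step 3 assume sizing on the pilot's observed difference. If the future trial instead takes only the usual-care rate from the pilot and sets its own 10-point target, a shift in the device arm leaves n unchanged. A 1 to 3 point shift in the usual-care rate (22% to 28% instead of 25%) then gives n = 221 to 277 against 250.

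**5. Scale against sampling error.** With 100 per arm, the standard error of the difference is √(0.25·0.75/100 + 0.15·0.85/100) = 5.6 points. The 95% interval is 10 ± 1.96 × 5.6, or −1 to +21 points. A shift of 1 to 3 points is 0.2 to 0.5 standard errors and could not be seen in the pilot's data.

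**6. The label (again assumed rates, and two different end-points).** Detecting a halving needs 278 per arm if progression is level 3 alone at 15%. If it is levels 2 and 3 together at 20% to 40%, it needs 199 down to 82, so the ratio is 1.4 to 3.4. Sampling error alone does about as much: 15 of 100 has a 95% Wilson interval of 9.3% to 23.3%, for which n runs from 470 down to 166, a ratio of 2.8.

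**The case against.** A reader might infer that the classifier knows the arm, because initial and follow-up data share one form and the database is open to the principal investigator, co-investigators and study coordinators. The documents do not support that. No passage says that allocation is recorded on the form or in the database. Randomization is controlled by a biostatistician who is not named in the access list. The blinded examiner could also be one of the investigators with access, and could be the person who assigns the level.

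Assignment during analysis can also be read harmlessly, as tabulating signs and decisions already recorded under blinding at the 48-hour visit. The Data Collection Form, where scoring rules or category boxes might sit, is not in the documents.

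The numbers are open to challenge too. The borderline share, the one-sided misplacement and the underlying rates are all invented. The fall to 55% power depends on sizing from the observed difference, and under the alternative in step 4 most of the effect disappears. The assumed shift is smaller than the pilot's sampling error, the pilot is descriptive, and no test or stopping rule is attached to the interim analysis.

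All of this stands against a claim of bias. It does not supply the missing rule. The plan does say when the primary outcome is classified, and it places that after the only step it masks. The descriptive design does not remove the issue either, since the rate is what the study is meant to deliver. On the label, the objection largely succeeds: if all three levels are tabulated by arm, either rate can be read off, and only the name is missing.

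**Conclusion.** The point holds as an avoidable risk of bias and should be fixed; confidence is moderate. The primary outcome category is assigned at a stage for which the protocol states neither a rule nor masking, so the blinded examination does not clearly protect what will be reported. It does not follow that the assignment is unmasked or that the pilot's rates will be biased. The documents are silent on masking at that step, and the form has not been seen.

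No size can be derived from the documents. The figures in steps 3 to 6 only illustrate that a shift too small to be visible in the pilot could matter if it were carried into a later sample size. They rest on assumed rates and, in step 3, on sizing from the observed difference. The missing label for progression, and the unstated link between level 3 and the referral sentence, are minor.

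**What to change.** **Section V, assignment.** Replace classification during data analysis with one of two methods:

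- the blinded examiner records the level at the 48-hour visit, as a judgement made then; or
- a fixed written rule derives it from the blinded findings.

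For subjects followed only by telephone, apply a written rule to the answers without arm codes. Lock the categories before arm codes are merged and, for subjects in the interim analysis, before that look.

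**Sections V and IX, label.** Before the interim analysis, name which level or levels count as progression, and tabulate all three levels by arm. Reconcile level 3 with the referral passage for analysis purposes only, with no change to care. If level 3 means treatment actually given after referral, say so, name the data source and cut-off date, and use the written rule.

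If the Data Collection Form already holds such rules, citing them in Section V and adding the lock and the label would be enough.

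**Cost.** Probably a few lines on the form and in the protocol, and keeping arm codes apart from outcome data until the lock. No new visit is needed. The real trade-off is that a level judged at the visit does not capture treatment started later, and the protocol must state that.
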